9.7 Statistical tests

Describe the statistical tests for analyzing the safety data to determine whether harms are occurring.

As we expect adverse events to be infrequent, we are not planning to do any interim safety analyses.

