3.3.2 Follow-up for withdrawn subjects

Describe when and how to withdraw subjects from the study; the type and timing of the data to be collected for withdrawal of subjects; whether and how subjects are to be replaced; the follow-up for subjects withdrawn from investigational treatment.

Study personnel will contact consenting parents by phone notifying them of their removal from the study and the reason for withdrawal. If the reason is due to failure-to-thrive, the infant's pediatrician will also be notified. If study personnel are unable to reach the consenting parent, a letter will be sent via US mail.

No further data will be collected on participants that are withdrawn, and these participants will not be replaced.

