8.3 Statistical methods

Describe the statistical methods (or non-statistical methods of analysis) that will be employed.

We will assess conditional weight gain from birth to 6 months to assess rapid infant growth.^{80,81} Conditional weight gain will be calculated as standardized residuals from the linear regression of weight for age at 6 months on weight for age at birth, with length for age at birth and 6 months and infant age at the 6-month visit entered as covariates. We will explore the moderating role of child sex, delivery mode, and maternal parity on intervention effects. Similar analyses will be conducted for the intervention period spanning ages 1-6 months.

For cross-sectional analyses at age 6 months, ANOVA will estimate the effects of intervention group on mean weight-for-length. Logistic regression will be used to compare intervention effects on the dichotomous outcome of overweight at 6 months.

For growth from 1-6 months, we will fit a repeated measures ANOVA of BMI, with visit and study group as within and between factors, respectively.

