9.3 Method of collection of safety information

Describe the method by which the safety information will be collected (e.g., with case report forms, at study visits, by telephone calls and with subjects).

Any growth failure event will be considered an adverse event, and these will be captured with a case report form.

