9.4 Frequency of data collection

Describe the frequency of data collection, including when safety data collection starts.

Data are collected per the visit schedules for the intervention and control groups.

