9.6 Frequency of review of cumulative data

Describe the frequency or periodicity of review of cumulative data.

Cumulative data will be reviewed at the end of the trial.

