9.8 Suspension of research

Describe any conditions that trigger an immediate suspension of research.

Suspension of the research would occur if:

1. >33% of participants are not adhering to the data collection procedures
2. >33% of intervention group participants meet criteria for failure-to-thrive
3. Attrition exceeds 33% after Visit 2

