10.0 Risks

List the reasonably foreseeable risks, discomforts, hazards, or inconveniences to the subjects related to the subjects' participation in the research. Include as may be useful for the IRB's consideration, a description of the probability, magnitude, duration and reversibility of the risks. Consider all types of risk including physical, psychological, social, legal, and economic risks. Note: Loss of confidentiality is a potential risk when conducting human subject research.

- If applicable, indicate which procedures may have risks to the subjects that are currently unforeseeable.
- If applicable, indicate which procedures may have risks to an embryo or fetus should the subject be or become pregnant.
- If applicable, describe risks to others who are not subjects.

It is possible that a reduction in formula intake could lead to temporary growth faltering (i.e. failure-to-thrive), though this would be self-limited and could be addressed by subsequently increasing formula intake.

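### Withdrawing infants at failure-to-thrive and checking the intervention arm more often distorts the failure-to-thrive comparison and shrinks the 6-month difference; no comparison method is given

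*Combined protocol and SAP*

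**What the plan says.** Section 10.0 names one risk: "It is possible that a reduction in formula intake could lead to temporary growth faltering (i.e. failure-to-thrive"). Section 3.3.1 makes failure-to-thrive a reason for removal. It is defined as weight-for-length below the 5th percentile, or as a downward crossing of more than two major centile lines; whether one or both are needed is not stated. Section 3.3.2 adds: "No further data will be collected on participants that are withdrawn, and these participants will not be replaced".

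The events are recorded in both arms. Section 9.3: "Any growth failure event will be considered an adverse event, and these will be captured with a case report form". Section 9.4 ties the timing to each arm's schedule: "Data are collected per the visit schedules for the intervention and control groups". Under 7.1 and 7.2 both arms are measured at 1, 2, 4 and 6 months, and only the intervention arm at 3 and 5 months.

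On analysis, 9.6 says "Cumulative data will be reviewed at the end of the trial" and gives no method. Section 9.7, where the template asks for the tests applied to safety data, answers "As we expect adverse events to be infrequent, we are not planning to do any interim safety analyses". Section 8.3 covers conditional weight gain, weight-for-length, BMI and overweight ("Logistic regression will be used to compare intervention effects on the dichotomous outcome of overweight at 6 months"), but not failure-to-thrive. The suspension rule in 9.8 counts one arm only: more than 33% "of intervention group participants meet criteria for failure-to-thrive".

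**The concern.** The intervention lowers recommended volume by 10% or 15% in heavier infants. The natural safety question is therefore whether failure-to-thrive is more common than under usual care. The data to answer it will exist, but the counting rule is open, and the two obvious rules err in opposite directions. Choosing between them after seeing the data means choosing the direction of the error. The shared-visit tally is the more troubling one because it can hide harm.

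Removal also depends on the outcome. Infants withdrawn for poor growth at months 2 to 5 have no 6-month measurement, so the lowest-growing infants drop out of the 6-month comparisons, and more of them drop out of the arm that is checked more often. Section 8.2 says the pilot data will be used to size a full trial, so both distortions could carry forward.

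**Working it through.** The plan gives no safety rate, SD or power, so there is no figure to reproduce.

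**Step 1: direction, from the visit schedule alone.** Suppose growth is identical in both arms and no visit is missed. Let
- C = proportion of controls flagged at month 2, 4 or 6;
- I = proportion of intervention infants flagged at any of months 2 to 6;
- S = proportion of intervention infants first flagged at month 2, 4 or 6;
- A = proportion first flagged at month 3 or 5, and so already withdrawn. Then I = S + A.

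Every infant counted in C would be counted in I, and every infant counted in S would be counted in C. So S ≤ C ≤ I. The excess I - C is infants flagged only at month 3 or 5. The shortfall C - S is infants first flagged at 3 or 5 who would have been flagged again at a later shared visit.

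**Step 2: size, under stated assumptions.** From the plan: 60 infants (8.1), the visit months (7.1) and the two criteria and seven centile lines (3.3.1). Assumed: 1:1 allocation (30 per arm); weight-for-length z normal with SD 1 and mean 0, 0.3 or 0.5; first-order autoregressive month-to-month correlation 0.8 to 0.98; infants below the 5th percentile at month 1 excluded; centile crossing counted on weight-for-length from month 1. I simulated 600,000 infants per setting. Selected results:

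| Mean, correlation, criterion | C | S | A | I | 30(I-C) | 30(S-C) |
|---|---|---|---|---|---|---|
| 0.3, 0.8, below 5th only | 5.0% | 3.9% | 2.5% | 6.4% | +0.43 | -0.3 |
| 0.3, 0.95, either | 3.9% | 2.8% | 1.7% | 4.5% | +0.19 | -0.3 |
| 0.3, 0.8, either | 15.5% | 10.5% | 8.2% | 18.7% | +0.98 | -1.5 |
| 0, 0.8, either | 18.0% | 12.4% | 9.4% | 21.8% | +1.1 | -1.7 |

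The last two columns use unrounded proportions. For row 1, the rounded figures give 30 × (0.064 - 0.050) = 0.42.

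Across settings with control failure-to-thrive of about 5% or less, the errors are +0.05 to +0.4 and -0.1 to -0.5 infant per 30. At correlation 0.98 the excess is only about 0.05 to 0.12, because persistent failure-to-thrive is caught at the next shared visit anyway. A variant that counts month 1 as a look and makes up to 20% of the variance measurement noise reaches +1.67, but there the control count is 8.17 of 30 (27%).

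**Step 3: effect on the 6-month difference.** Lower every intervention infant by 0.3 z from month 2. Withdraw flagged infants at months 2 to 5 (intervention) and months 2 and 4 (control). Keep failure-to-thrive first seen at Visit 7.
- Plan's schedules: the true -0.30 appears as about -0.14 to -0.25.
- Same, with the fall building up to month 6: about -0.18 to -0.27.
- Abrupt fall with both arms checked only at 2 and 4: about -0.23 to -0.28.

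The split of the loss varies. At mean 0, correlation 0.8, either criterion, the results are -0.14 (plan) and -0.24 (equal schedules): a loss of 0.16, of which 0.06 arises even with equal visits and 0.10 from the extra visits. At mean 0, correlation 0.95, below the 5th only, they are -0.20 and -0.24: a loss of 0.10, of which 0.06 arises with equal visits.

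**Step 4: sampling error.** With SD 1 and 30 per arm, the standard error of a mean difference is √(2/30) = 0.26, larger than the greatest loss above (0.16). For counts, the exact 97.5% upper limit after 0 of 30 is 1 - 0.025^(1/30) = 11.6%.

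**The case against.** The strongest reply is that this is a 60-infant feasibility pilot with adequate individual protection. Growth is reviewed in real time (9.1), events go on a case report form (9.3), the pediatrician is told (3.3.2), cumulative data are reviewed at the end (9.6), and ordinary well-child care continues (15.4). A table by arm can be made from data already collected, and its natural all-visit form errs towards overstating harm. All of this is fair, and it limits the stakes. It does not settle which count to use, and after withdrawal the well-child measurements are not study data.

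The sizes also rest on assumed growth. The larger errors need control failure-to-thrive of 14-18%, which does not fit the infrequent events that 9.7 expects. That stands, so the low-rate range is the one to carry.

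Three stronger readings are tempting, and the documents do not support them:
- That the plan excludes any safety comparison. Section 9.7 rules out interim analyses only; the gap is that no final method appears in 8.3, 9.6 or 9.7.
- That failure-to-thrive goes unrecorded in controls. Sections 9.3 and 9.4 cover both groups.
- That the unequal visits cause all of the shrinkage at 6 months. Part of it occurs with equal schedules, because removal depends on growth.

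**Conclusion.** The point holds as a worthwhile, inexpensive correction; it is not a fatal flaw. The missing comparison, the unequal checks and the removal rule follow from the text. The direction of both tally errors follows from the schedule alone when growth is identical and no visits are missed.

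The sizes in the working depend on its assumed means, SD, correlations and 1:1 allocation. At plausible low event rates each tally is off by less than about half an infant per 30, which is small beside sampling error. The attenuation was worked out for weight-for-length z. The primary endpoint, conditional weight gain, also needs a 6-month weight and loses the same infants, but the size of its bias was not calculated.

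**What to change.** **Main change, in 3.3.2.** Failure-to-thrive stops the volume advice but not follow-up. Routine 2-, 4- and 6-month well-child weights and lengths are still recorded, and these infants are included in the 6-month analyses in 8.3. This removes the loss of low-growing infants and the visit-schedule bias in a count over shared visits. One limit remains: an infant flagged at month 3 or 5 may recover before the next shared visit because the advice stopped, so those detections must stay visible.

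**With it, in 9.7.** Add one descriptive end-of-trial table by arm: infants meeting a 3.3.1 failure-to-thrive criterion at the shared 2-, 4- and 6-month visits, an exact 95% interval for the difference, and month-3 and month-5 detections on a separate line. State whether either criterion suffices, and which WHO chart and starting measurement apply to centile crossing.

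**Cost.** An amendment, consent wording and one table; the measurements are already part of usual care. Intervals will be wide at about 30 per arm, so the table describes and does not test.

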9.8 Suspension of research

Describe any conditions that trigger an immediate suspension of research.

Suspension of the research would occur if:

1. >33% of participants are not adhering to the data collection procedures
2. >33% of intervention group participants meet criteria for failure-to-thrive
3. Attrition exceeds 33% after Visit 2

10.0 Risks

List the reasonably foreseeable risks, discomforts, hazards, or inconveniences to the subjects related to the subjects' participation in the research. Include as may be useful for the IRB's consideration, a description of the probability, magnitude, duration and reversibility of the risks. Consider all types of risk including physical, psychological, social, legal, and economic risks. Note: Loss of confidentiality is a potential risk when conducting human subject research.

- If applicable, indicate which procedures may have risks to the subjects that are currently unforeseeable.
- If applicable, indicate which procedures may have risks to an embryo or fetus should the subject be or become pregnant.
- If applicable, describe risks to others who are not subjects.

It is possible that a reduction in formula intake could lead to temporary growth faltering (i.e. failure-to-thrive), though this would be self-limited and could be addressed by subsequently increasing formula intake.

11.0 Potential Benefits to Subjects and Others

11.1 Potential Benefits to Subjects

Describe the potential benefits that individual subjects may experience from taking part in the research. If there is no direct benefit to subjects, indicate as such. Compensation is not considered a benefit. Compensation should be addressed in section 13.0.

The study intervention could improve infant growth trajectories, reduce rapid infant weight gain, and reduce likelihood of overweight during infancy and beyond for participants.

11.2 Potential Benefits to Others

Include benefits to society or others.

This pilot could inform formula feeding guidelines for infants in clinical care and in clinical research trials.

12.0 Sharing Results with Subjects

Describe whether results (study results or individual subject results, such as results of investigational diagnostic tests, genetic tests, or incidental findings) will be shared with subjects or others (e.g., the subject's primary care physicians) and if so, describe how information will be shared.

Parents of individual participants will receive real-time data on their infant's growth, consistent with clinical care.

13.0 Subject Payment and/or Travel Reimbursements

Describe the amount, type (cash, check, gift card, other) and timing of any subject payment or travel reimbursement. If there is **no** subject payment or travel reimbursement, indicate as not applicable.

Extra or Course Credit: Describe the amount of credit **and** the available alternatives. Alternatives should be equal in time and effort to the amount of course or extra credit offered. It is not acceptable to indicate that the amount of credit is to be determined or at the discretion of the instructor of the course.

Approved Subject Pool: Indicate which approved subject pool will be used; include in response below that course credit will be given and alternatives will be offered as per the approved subject pool procedures.

Participating parents randomized to the intervention group will receive up to \$300 for participation in the study; control participants who have 2 less study visits will receive up to \$250 for participation. Following Visit 2, they will receive \$50 for successful completion of the visit and study surveys. \$25 will be given following visits 3-6 (note no visit 4 and 6 for controls). Upon completion of Visit 7's anthropometrics and survey data collection, participants will receive \$150.

14.0 Economic Burden to Subjects

14.1 Costs

Describe any costs that subjects may be responsible for because of participation in the research.

Research participants will not accrue any additional costs as a result of their participation.

14.2 Compensation for research-related injury

If the research involves more than Minimal Risk to subjects, describe the available compensation in the event of research related injury.

If there is no sponsor agreement that addresses compensation for medical care for research subjects with a research-related injury, include the following text as written - DO NOT ALTER OR DELETE:
It is the policy of the institution to provide neither financial compensation nor free medical treatment for research-related injury. In the event of injury resulting from this research, medical treatment is available but will be provided at the usual charge. Costs for the treatment of research-related injuries will be charged to subjects or their insurance carriers.

For sponsored research studies with a research agreement with the sponsor that addresses compensation for medical care for research-related injuries, include the following text as written - DO NOT ALTER OR DELETE:

It is the policy of the institution to provide neither financial compensation nor free medical treatment for research-related injury. In the event of injury resulting from this research, medical treatment is available but will be provided at the usual charge. Such charges may be paid by the study sponsor as outlined in the research agreement and explained in the consent form.

It is the policy of the institution to provide neither financial compensation nor free medical treatment for research-related injury. In the event of injury resulting from this research, medical treatment is available but will be provided at the usual charge. Costs for the treatment of research-related injuries will be charged to subjects or their insurance carriers.

15.0 Resources Available

15.1 Facilities and locations

Identify and describe the facilities, sites and locations where recruitment and study procedures will be performed.

If research will be conducted outside the United States, describe site-specific regulations or customs affecting the research, and describe the process for obtaining local ethical review. Also, describe the principal investigator's experience conducting research at these locations and familiarity with local culture.

This research will be conducted on the maternity/nursery floors of Penn State Children's Hospital and at the ambulatory clinics affiliated with the Division of Academic General Pediatrics.

Penn State Children's Hospital maternity/nursery floors - ~2000 infants are delivered annually on the floor. All mother-baby dyads on the well newborn service have private rooms. Recruitment and enrollment procedures are expected to occur frequently on this unit (6th and 7th floors).

Ambulatory Clinics – The Division of Academic General Pediatrics performs >50,000 visits annually at its clinics located at Hope Drive, Elizabethtown, and Nyes Road. These clinics are accustomed to research. Recruitment and enrollment may also occur at the clinics, and monthly anthropometrics and data collection will occur, typically as part of well child care visit.

15.2 Feasibility of recruiting the required number of subjects

Indicate the number of potential subjects to which the study team has access. Indicate the percentage of those potential subjects needed for recruitment.

With ~2000 well newborns delivered annually, it is expected that ~30% will be exclusively formula fed. Among these 600, it is expected that ~200-300 will meet the remaining inclusion/exclusion criteria, providing an ample pool of participants.

15.3 PI Time devoted to conducting the research

Describe how the PI will ensure that a sufficient amount of time will be devoted to conducting and completing the research. Please consider outside responsibilities as well as other on-going research for which the PI is responsible.

[name] has a long track-record of conducting clinical research and devoting appropriate time to his research studies despite other obligations including patient care and administration.

15.4 Availability of medical or psychological resources

Describe the availability of medical or psychological resources that subjects might need as a result of their participation in the study, if applicable.

Participating infants will receive their typical infant well child care from their pediatricians.

15.5 Process for informing Study Team

Describe the training plans to ensure members of the research team are informed about the protocol and their duties, if applicable.

All study team members will have completed the appropriate training prior to the initiation of the study. Team meetings will occur at least monthly via Zoom.

16.0 Other Approvals

16.1 Other Approvals from External Entities

Describe any approvals that will be obtained prior to commencing the research (e.g., from engaged cooperating institutions IRBs who are also reviewing the research and other required review committees, community leaders, schools, research locations where research is to be conducted by the Penn State investigator, funding agencies, etc.).

N/A

16.2 Internal PSU Committee Approvals

Check all that apply:

- Anatomic Pathology – **Penn State Health only** – Research involves the collection of tissues or use of pathologic specimens. Upload a copy of “HRP-902 - Human Tissue For Research Form” in CATS IRB.
- Animal Care and Use – **All campuses** – Human research involves animals and humans or the use of human tissues in animals
- Biosafety – **All campuses** – Research involves biohazardous materials (human biological specimens in a PSU research lab, biological toxins, carcinogens, infectious agents, recombinant viruses or DNA or gene therapy).
- Clinical Laboratories – **Penn State Health only** – Collection, processing and/or storage of extra tubes of body fluid specimens for research purposes by the Clinical Laboratories; and/or use of body fluids that had been collected for clinical purposes but are no longer needed for clinical use. Upload a copy of “HRP-901 - Human Body Fluids for Research Form” in CATS IRB.

- Clinical Research Center (CRC) Advisory Committee – **All campuses** – Research involves the use of CRC services in any way.
- Conflict of Interest Review – **All campuses** – Research has one or more of study team members indicated as having a financial interest.
- Radiation Safety – **Penn State Health only** – Research involves research-related radiation procedures. All research involving radiation procedures (standard of care and/or research-related) must upload a copy of “HRP-903 - Radiation Review Form” in CATS IRB.
- IND/IDE Audit – **All campuses** – Research in which the PSU researcher holds the IND or IDE or intends to hold the IND or IDE.
- Scientific Review – **Penn State Health only** – All investigator-written research studies requiring review by the convened IRB must provide documentation of scientific review with the IRB submission. The scientific review requirement may be fulfilled by one of the following: (1) external peer-review process; (2) department/institute scientific review committee; or (3) scientific review by the Clinical Research Center Advisory committee. NOTE: Review by the Penn State Health Cancer Institute (PSCI) Protocol Review Committee or the PSCI Disease Team is required if the study involves cancer prevention studies or cancer patients, records and/or tissues. For more information about this requirement see the IRB website.
- St. Joseph Administrative Review – **Penn State Health only** – Penn State Health Research that will be conducted at St. Joseph Medical Center or St. Joseph Community Medical Groups.

